### **ITT: LAST STATUS, PD AND DEATHS**

Table 51: Progression, Death. ITT

Cohort	
Progression type	
Only IntraPD	
No PD	
Both	
Only ExtraPD	
Death	
No	
Yes	

# PP: LAST STATUS, PD AND DEATHS

Table 52: Progression, Death. PP

Cohort
Progression type
Only IntraPD
No PD
Both
Only ExtraPD
Death
No
Yes

Table 53: Last available status

Number Cohort Intention to treat PP available Propulation	ast Last ilable available atus date	End Date of Treatment Date	Intracraneal Progression disease	Date Date of of PD death	End Trial Date
---	---	----------------------------	--	--------------------------	----------------------

# 4.5. INTRACRANIAL OVERALL SURVIVAL (IOS). 4.5.1.ITT ALL PATIENTS: INTRACRANIAL OVERALL SURVIVAL (IOS).

Table 54: Events type OS

os	N	%	95%CI
Alive			
Death			
Total			

Table 55: Median/mean OS (estimated by Kaplan-Meier)

	Median (months)	CI 95%	Mean	CI 95%
Overall survival				

Table 56: OS estimated survival ratio

os	Events (%, total N)	Patients at risk	% estimated cumulative survival ratio	CI 95%
At 6 months At 12 months At 18 months At 24 months				

Figure 5: Overall survival

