# 3.5. TREATMENT COMPLIANCE

Upon database closure, there are 4 patients still undergoing treatment.

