# 4.5.2.ITT - COHORT 1: INTRACRANIAL OVERALL SURVIVAL (IOS).

Table 57: Events type OS

os	N	%	95%CI
Alive			
Death			
Total			

Table 58: Median/mean OS (estimated by Kaplan-Meier)

	Median (months)	CI 95%	Mean	CI 95%
Overall survival				

Table 59: OS estimated survival ratio

os	Events (%, total N)	Patients at risk	% estimated cumulative survival ratio	CI 95%
At 6 months At 12 months At 18 months At 24 months				

Figure 6: Overall survival

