# 4.7.1.ITT ALL PATIENTS: EXTRACRANIAL PROGRESSION-FREE SURVIVAL (EPFS).

Table 90: Events type PFS

PFS (event)	N	%	95%CI
Censored			
Event (PD/death)			
Total			

Table 91: Median/mean PFS (estimated by Kaplan-Meier)

	Median (months)	CI 95%	Mean	CI 95%
Progression free survival				

Table 92: PFS estimated survival ratio

PFS	Events (%, total N)	Patients at risk	% estimated cumulative survival ratio	CI 95%
At 6 months At 12 months At 18 months At 24 months				

Figure 11: Progression free survival

4.7.2.ITT - COHORT 1: EXTRACRANIAL PROGRESSION-FREE SURVIVAL (EPFS).

Table 93: Events type PFS

PFS (event)	N	%	95%CI
Censored			
Event (PD/death)			
Total			

Table 94: Median/mean PFS (estimated by Kaplan-Meier)

	Median (months)	CI 95%	Mean	CI 95%
Progression free survival				

Table 95: PFS estimated survival ratio

PFS	Events (%, total N)	Patients at risk	% estimated cumulative survival ratio	CI 95%
At 6 months At 12 months At 18 months At 24 months				

Figure 12: Progression free survival

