#### 7.1.3. INTRACRANIAL OVERALL SURVIVAL (IOS) VS SYMPTOMATIC.

Table 153: Events type OS

Symptomatic group		
Death		
Alive		

1. Pearson's Chi-squared test

Table 154: Median/mean OS (estimated by Kaplan-Meier)

	Median (months)	CI 95%	Mean	CI 95%
No				
Yes				

Table 155: OS estimated survival ratio

os	Events (%, total N)	Patients at risk	% estimated cumulative survival ratio	CI 95%
No				
At 6 months				
At 12				
months				
At 18				
months				
At 24				
months				
Yes				
At 6 months				
At 12				
months				
At 18				
months				
At 24				
months				

Figure 20: Overall survival vs Symptomatic group

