## 7.2.3. INTRACRANIAL PROGRESSION-FREE SURVIVAL (IPFS) VS SYMPTOMATIC.

Table 162: Events type PFS

Symptomatic group	
Event (PD/death)	
Censored	

1. Pearson's Chi-squared test

Table 163: Median/mean PFS (estimated by Kaplan-Meier)

	Median (months)	CI 95%	Mean	CI 95%
No				
Yes				

Table 164: PFS estimated survival ratio

PFS	Events (%, total N)	Patients at risk	% estimated cumulative survival ratio	CI 95%
No				
At 6 months				
At 12				
months				
At 18				
months				
At 24				
months				
Yes				
At 6 months				
At 12				
months				
At 18				
months				
At 24				
months				

Figure 23: Progression-free survival vs Symptomatic group

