#### 2.2. OS ON ITT ACCORDING TO RADIOTHERAPY

Table 6: Events type OS

Radiotherapy	
Death	
Alive	

1. Pearson's Chi-squared test

Table 7: Median/mean OS (estimated by Kaplan-Meier)

	Median (months)	CI 95%	Mean	CI 95%
No				
Yes				

Table 8: OS estimated survival ratio

os	Events (%, total N)	Patients at risk	% estimated cumulative survival ratio	CI 95%
No				
At 6 months				
At 12				
months				
At 18				
months				
At 24				
months				
Yes				
At 6 months				
At 12				
months				
At 18				
months				
At 24				
months				

Figure 25: Overall survival vs Radiotherapy

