#### 2.3. IPFS ON ITT ACCORDING TO RADIOTHERAPY

Table 9: Events type PFS

Radiotherapy	
PFS Event	
PD	
Censored	
Death (without previous PD)	

1. Pearson's Chi-squared test

Table 10: Median/mean PFS (estimated by Kaplan-Meier)

	Median (months)	CI 95%	Mean	CI 95%
No				
Yes				

Table 11: PFS estimated survival ratio

PFS	Events (%, total N)	Patients at risk	% estimated cumulative survival ratio	CI 95%
No				
At 6 months				
At 12 months At 18				
months At 24				
months Yes				
At 6 months				
At 12 months				
At 18 months				
At 24 months				

Figure 26: Progression free survival vs Radiotherapy

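### Kaplan-Meier mean survival is tabulated with no truncation time, so wherever a group's longest time is censored it is a restricted mean to an unstated limit

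*Combined protocol and SAP*

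**What the plan says.** The SAP tabulates a mean with its own 95% CI next to the Kaplan-Meier median in these places:

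- OS, section 4.5: Tables 55, 58, 61, 64, 67 and 70, e.g. "Table 55: Median/mean OS (estimated by Kaplan-Meier" and, for cohort 1, "Table 58: Median/mean OS (estimated by Kaplan-Meier".
- Extracranial PFS, section 4.7: Tables 91, 94, 97, 100, 103 and 106, e.g. "Table 91: Median/mean PFS (estimated by Kaplan-Meier".
- Symptomatic-group analyses, sections 7.1 and 7.2: Tables 148, 151, 154, 157, 160 and 163.
- Supplementary tables after the SAP, sections 2.2 to 2.4: Tables 7, 10 and 13.

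Two groups appear in one table in "Table 154: Median/mean OS (estimated by Kaplan-Meier" and "Table 163: Median/mean PFS (estimated by Kaplan-Meier", in the radiotherapy tables "Table 7: Median/mean OS (estimated by Kaplan-Meier" and "Table 10: Median/mean PFS (estimated by Kaplan-Meier", and in supplementary Table 13 (extracranial PFS by symptomatic group).

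No section gives a truncation time, calls the mean restricted, or says how a curve ending in a censored time is handled. Censoring is part of the plan: SAP sections 4.6 and 4.7 censor event-free patients at their last tumour assessment, and the OS tables have a row for patients alive. SAP section 3.5 adds: "Upon database closure, there are 4 patients still undergoing treatment". Protocol section 10.6 plans Kaplan-Meier estimates at chosen time points and curves. It does not mention a mean.

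**The concern.** The mean survival time is the whole area under the survival curve. If the largest time in a group is an event, the Kaplan-Meier curve falls to zero and the area is complete. If that time is censored, the curve stops above zero and the data say nothing about the area beyond. What is then printed is the area up to some limit, and its CI refers to that partial area.

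Without a stated limit, a reader cannot tell what has been estimated. A common convention is to stop at the group's own longest observed time. The figure then depends on length of follow-up and group size as well as on survival, and part of a difference between two adjacent means could come from the limits alone.

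**Working it through.** The documents state no value for mean survival, so there is no figure of the plan's to reproduce.

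**Inputs from the documents.** Recruitment of 36 months and follow-up of 24 months (protocol section 8.3) give 24 to 60 months of potential follow-up by entry date. Protocol section 8.1 describes survival contacts as running to 24 months or study closure, which leaves open a reading in which everyone stops at 24 months. Cohort sizes are 48 and 15 (synopsis). Protocol section 2.3 cites a median OS of about 9 months with treatment.

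**Assumptions.** Exponential survival; uniform entry; medians of 12, 18 and 24 months in addition to 9.

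**Step 1: size of a known cut.** With m = median / ln 2, the mean restricted to τ is m(1 − exp(−τ/m)).

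- Median 12: m = 12/0.693 = 17.3 months. At τ = 24, two medians, 17.3 × (1 − 0.25) = 13.0. At τ = 36 and 60 the results are 15.1 and 16.8.
- Median 18: m = 26.0 months. At τ = 24, 36 and 60 the results are 15.7, 19.5 and 23.4.

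**Step 2: the Kaplan-Meier mean under 24 to 60 months of follow-up.** The area was taken to the last observed time, with 4,000 simulated trials per setting.

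| Median | True mean | Mean, n=48 | Bias | Longest time censored, n=48 | Mean, n=15 | Bias | Longest time censored, n=15 |
|---|---|---|---|---|---|---|---|
| 9 | 12.98 | 12.67 | −2.4% | 49% | 12.55 | −3.3% | 36% |
| 12 | 17.31 | 16.51 | −4.6% | 65% | 16.24 | −6.2% | 53% |
| 18 | 25.97 | 23.00 | −11.4% | 86% | 22.41 | −13.7% | 72% |
| 24 | 34.62 | 27.96 | −19.3% | 91% | 27.29 | −21.2% | 81% |

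The average gap between n=48 and n=15 is 0.12, 0.27, 0.59 and 0.67 months, so below one month throughout.

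**Step 3: everyone stopped at 24 months.** At n=48 the means are 10.92, 12.98, 15.67 and 17.30 months, a bias of −15.9%, −25.0%, −39.7% and −50.0%. At n=15 they are 11.01, 13.01, 15.70 and 17.33, so group size now makes almost no difference.

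**Step 4: what one data set could show.** With median 18 and follow-up of 24 to 60 months, the longest observed time has a 5% to 95% range of 34.7 to 58.8 months at n=15 and 46.9 to 59.6 at n=48. Take two groups with that same hazard, one cut at 40 months and the other at 58:

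- 26.0 × (1 − exp(−40/26.0)) = 20.4 months
- 26.0 × (1 − exp(−58/26.0)) = 23.2 months

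The gap of 2.8 months comes from the limits alone.

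**Step 5: a common limit.** With τ = 24 for every group and at least 24 months of potential follow-up, the simulated restricted means for n=15, 48 and 63 agree within 0.1 month at each median.

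**The case against.** A reader might infer that the SAP formally compares means, that each group is cut at its own longest follow-up, and that every printed mean is therefore too low and not comparable. The documents do not support that.

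- **No test of means is planned.** Tables 154 and 163 and the supplementary tables only display the means together. The footnoted test in the accompanying event tables is a chi-squared test on event counts. Table 55 has a single group.
- **The cut is not stated.** A group-specific limit is a common convention, but the SAP does not adopt it, and a common limit remains possible.
- **The longest time may be an event.** Four patients still on treatment means some OS times are censored, not that the longest one is. Nor does it establish PFS censoring, because the protocol allows treatment beyond progression with sponsor agreement. At median 12, the longest time is an event in 35% of simulated trials at n=48 and 47% at n=15.
- **The two harms do not peak together.** The largest bias needs everyone cut at 24 months, and unequal limits then nearly disappear. At the 9-month median in the protocol's background, with 24 to 60 months of follow-up, the bias is 2% to 3%.
- **Little depends on the means.** Medians and Kaplan-Meier rates with numbers at risk are tabulated alongside, Table 50 gives reverse-censoring follow-up, and the main intracranial PFS tables (section 4.6) give only medians.

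All of this stands and keeps the point small. The missing limit remains: from the SAP alone, a reader cannot say what the mean or its CI estimates.

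**Conclusion.** The point holds as a minor one. The mean is undefined in the SAP, and whenever a group's longest time is censored it is a restricted mean to an unstated limit that understates the true mean. Under exponential survival and 24 to 60 months of potential follow-up, the understatement at n=48 is about 2% to 5% for medians of 9 to 12 months and 11% to 19% for medians of 18 to 24 months. The range of 16% to 50% applies only if follow-up ends at 24 months for all.

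Side-by-side means may rest on different limits. Group size alone produces an average gap below one month, but a single data set could show more, as the 2.8-month example illustrates. The simulated sizes are those of the two cohorts; the documents do not give the sizes of groups A+C and B or of the radiotherapy groups. The primary endpoint, medians and landmark rates are not affected, and no decision rule uses a mean.

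**What to change.** Delete the mean and its CI from the tables listed above. Medians and landmark rates are already reported, so nothing needed is lost, and the cost is one column per table.

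If a mean is wanted, report restricted mean survival time with its CI, labelled as such, and state the limit. Use one limit per endpoint for all groups shown, no later than the shortest of those groups' longest follow-up times. Twenty-four months, the last landmark in the OS tables, suits only endpoints where every group's curve reaches it. That should be checked for PFS: extracranial PFS landmarks for cohort 2 stop at 15 months (Tables 98 and 107) and intracranial PFS landmarks for A+C stop at 21 months (Table 158), although Table 164 lists 24 months for both symptomatic groups. The cost is one parameter in the code and a sentence in the SAP.

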# 4.5.2.ITT - COHORT 1: INTRACRANIAL OVERALL SURVIVAL (IOS).

Table 57: Events type OS

os	N	%	95%CI
Alive			
Death			
Total			

Table 58: Median/mean OS (estimated by Kaplan-Meier)

	Median (months)	CI 95%	Mean	CI 95%
Overall survival				

Table 59: OS estimated survival ratio

os	Events (%, total N)	Patients at risk	% estimated cumulative survival ratio	CI 95%
At 6 months At 12 months At 18 months At 24 months				

Figure 6: Overall survival

# 4.5.3.ITT - COHORT 2: INTRACRANIAL OVERALL SURVIVAL (IOS).

Table 60: Events type OS

os	N	%	95%CI
Alive			
Death			
Total			

Table 61: Median/mean OS (estimated by Kaplan-Meier)

	Median (months)	CI 95%	Mean	CI 95%
Overall survival				

Table 62: OS estimated survival ratio

os	Events (%, total N)	Patients at risk	% estimated cumulative survival ratio	CI 95%
At 6 months At 12 months At 18 months At 24 months				

Figure 7: Overall survival

# 4.5.4.PP ALL PATIENTS: INTRACRANIAL OVERALL SURVIVAL (IOS).

Table 63: Events type OS

os	N	%	95%CI
Alive			
Death			
Total			

Table 64: Median/mean OS (estimated by Kaplan-Meier)

	Median (months)	CI 95%	Mean	CI 95%
Overall survival				

Table 65: OS estimated survival ratio

os	Events (%, total N)	Patients at risk	% estimated cumulative survival ratio	CI 95%
At 6 months At 12 months At 18 months At 24 months				

Figure 8: Overall survival

# 4.5.5.PP - COHORT 1: INTRACRANIAL OVERALL SURVIVAL (IOS).

Table 66: Events type OS

OS	N	%	95%CI
Alive			
Death			
Total			

Table 67: Median/mean OS (estimated by Kaplan-Meier)

	Median (months)	CI 95%	Mean	CI 95%
Overall survival				

Table 68: OS estimated survival ratio

os	Events (%, total N)	Patients at risk	% estimated cumulative survival ratio	CI 95%
At 6 months				
At 0 months				
months				
At 18				
months				
At 24				
months				

Figure 9: Overall survival

# 4.5.6.PP - COHORT 2: INTRACRANIAL OVERALL SURVIVAL (IOS).

Table 69: Events type OS

os	N	%	95%CI
Alive			
Death			
Total			

Table 70: Median/mean OS (estimated by Kaplan-Meier)

	Median (months)	CI 95%	Mean	CI 95%
Overall survival				

Table 71: OS estimated survival ratio

os	Events (%, total N)	Patients at risk	% estimated cumulative survival ratio	CI 95%
At 6 months At 12 months At 18 months At 24 months				

Figure 10: Overall survival

# 4.6. INTRACRANIAL PROGRESSION-FREE SURVIVAL (IPFS).

Intracranial Progression-free survival (PFS), defined as the time from inclusion (first dose of treatment) until intracranial tumour progression (RECIST 1.1) or death. Patients without any of the previous events are censored at the date of the last available tumor assessment.

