Thus, COMBI-MB supports the use of dabrafenib and trametinib also in BRAF mutant melanoma patients with brain metastases. However, one of the main critics to this study, is the apparently short progression free survival in the main cohort (cohort A, patients asymptomatic) in comparison with patients treated in other clinical trials with the same combination and no brain metastases: 5.6 months in COMBI MB versus 11 months in COMBI-D. One of the reasons could be the well-known poorer prognosis of these patients, but another one could be the fact that patients in this clinical trial, were not allowed by protocol to be treated with a local therapy (except for previously treated ones in cohort B, C and D, but always before the dabrafenib and trametinib). For those patients achieving a non-complete response, it is unknown if further local therapy (radiation, radiosurgery, surgery) could improve the duration of the responses.

Combination or sequencing of systemic (targeted) and local treatment with radiation has demonstrated a manageable toxicity profile, with some concerns regarding radio necrosis and increase in dermatitis. Most of these data, however, come from retrospective case series.

Finally, although encorafenib in combination with binimetinib is indicated for the treatment of adult patients with unresectable or metastatic melanoma with a BRAF V600 mutation, it is unknown the activity in patients with BRAF mutant melanoma and brain metastases.

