## 5.3. Patient Inclusion and Cohort Assignment

During the screening (28 days before day 1 cycle 1) it should be assessed whether the patient is symptomatic (cohort 2) or asymptomatic (cohort 1).

Definition of Asymptomatic (cohort 1):.Patients without active symptoms secondary to brain metastases at the moment of inclusion.

After confirming that a patient fulfils all eligibility criteria of the study (inclusion/exclusion criteria), site staff will initiate the eCRF registration procedure.

Once procedure is fulfilled the site staff will receive the "Inclusion confirmation communication", and protocol-specific treatment can be initiated.

This is an open label, single arm study including two cohorts of patients, in each cohort, patients will be treated with encorafenib 450 mg once daily and binimetinib 45 mg twice daily.

After 56 days of treatment, a contrast enhanced brain MRI and CT body scan will be performed as first tumour assessment:

- Patients with PD at first evaluation in brain MRI (modified RECIST 1.1 criteria) and /or body CT scan (RECIST 1.1 criteria) will discontinue study treatment and will continue in the study for OS follow-up.
- Patients with CR in brain (modified RECIST 1.1) and no PD in the body (RECIST 1.1), will continue study treatment and will be followed every two months with contrast enhanced brain MRI and body CT scan up to 12 months. If no PD after one year, patients will be followed as per institutional criteria, and continue with the treatment.
  - o If considered by the investigator, local treatment can be done for brain CR patients, but only after confirming no safety concerns (defined as substantial deterioration of vital signs (including ECOG PS), physical examination, ECG, Lab. Values that do not recommend RT) with the three first patients treated with radiation therapy in the running phase (for more information, please see section 9.1).
- Patients with no CR and no PD in brain MRI per modified RECIST 1.1 criteria, and no PD in body per RECIST 1.1 criteria, will be treated with local RT and/or radiosurgery, and then will continue Enco and Bini. The first 3 patients will be treated in a running

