- After progression, patients will be followed only for overall survival.
  - o In case of encorafenib and binimetinib are providing a clinical benefit to any patient, treatment could be continued after discussion with Sponsor if it agrees on that. In this case, follow up will be done as per institutional criteria. In the study, these patients will be followed only for overall survival.
- Study assessments: in each monthly visit, adverse events will be registered, blood samples will be collected for blood cell counts and general biochemistry (including magnesium, potassium and creatinine-kinases); an ECG will be performed at baseline, after one month of treatment, and every 3 months thereafter; a left ventricular ejection fraction (LVEF) evaluation will be performed by as per institutional guidelines at baseline and every 3 months thereafter ophthalmologic anamnesis and evaluation will be performed by oncologist at baseline and in every monthly visit, if there's any alarm symptom or sign, patient will be evaluated by Ophthalmologist. Body CT-scan and contrast enhanced brain MRI will be performed baseline and every 8 weeks up to 12 months and according to normal practise thereafter. More information regarding study determination is provided in section 8 of this protocol.

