#### Non-radiological Assessments

Visible cutaneous lesions must be measured clinically. Digital and standardized photographic images including a ruler for scale as part of the image are recommended for documentation. All clinical assessments must be performed within proximity (± 7 days) of any protocol specified radiographic assessments

**Safety evaluation:** Safety assessments and adverse events include tumour-related, unrelated and treatment-related signs and symptoms. Adverse events will be documented and recorded in the CRF upon patient notification. AEs will be collected from the signing of Informed Consent until the end of treatment visit (30 days after end of treatment) or up to resolution. Classification of toxicity will be done according to the common terminology criteria for adverse events of the National Cancer Institute, version 4.03 (NCI CTCAE v. 4.03).

**PFS follow-up:** Body CT-scan and contrast enhanced brain MRI will be performed baseline and every 8 weeks (+/-1 week) up to 12 months and according to normal practice thereafter **until disease progression**, **independently of the end of treatment reason if it was not the documentation of disease progression**.

**OS Follow-up:** After disease progression all patients will be monitored to determine subsequent antineoplastic treatments and survival. It is recommended to maintain contacts by phone or by other methods every 4 weeks to carry out timely follow-up (up to 24 months or study closure).

**New anti-cancer therapy:** Information on subsequent treatments should include the list of post-treatment treatments, the drugs administered, and the date of initiation and discontinuation of each drug. All data will be recorded in the medical record and in the eCRF.

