# e) Follow-up before progression disease

- ECOG performance status
- Neurologic examination and Modified Barthel Index
- Haematology, coagulation, serum biochemistry, and pregnancy test (urine test and in case this test be positive, a serum pregnancy test should be done to confirm no pregnancy.), (only if patient it's on treatment)
- CT Scan (every two months up to 12 months, thereafter patients will be assessed as per institutional criteria)
- Contrast enhanced brain MRI (every two months up to 12 months, thereafter patients will be assessed as per institutional criteria)
- Colour Digital Photography (including a metric ruler) of the skin lesions (every two months up to 12 months, thereafter patients will be assessed as per institutional criteria).

After one year of 1st day of treatment, follow up will be performed according local normal practise.

f) Follow-up before progression disease after ending treatment:

- Subjects who no longer receive study treatment due to progression should remain in follow-up until their death or until the closure of the study (whichever comes first).
- Subjects who no longer receive study treatment due to unacceptable toxicity or at the discretion of the investigator should remain in follow up until progression. Visits will be scheduled every 8 weeks and tumor evaluation should be performed every 8 weeks until tumor progression the fist year, and after 12 months, the tumor evaluation can be done as per institutional criteria. The tests and questionnaires can be done according to the normal practise too.
- Subjects who have switched to an alternative treatment do not perform a formal follow-up, except to record the date of the death.

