performed within 6 months after database closure expected at 24 months after last patient inclusion, however interim analysis might be performed when analysing other primary variables

Percentage of patients (%) free of extracraneal progression at 6 (week 24), 12 (week 28) and 24 months (week 96): percentage of patients free of progression by RECIST 1.1 at 6 months (week 24), 12 months (week 48) and 24-month (week 96) considering date of inclusion. The final statistical analysis of this endpoint is expected to be performed within 6 months after database closure expected at 24 months after last patient inclusion, however interim analysis might be performed when analysing other primary variables.

**Overall Survival in both cohorts (OS):** OS is calculated as the time from date of inclusion to date of death due to any cause. The final statistical analysis of this endpoint is expected to be performed within 6 months after database closure expected at 24 months after last patient inclusion, however interim analysis might be performed when analysing other primary variables.

Percentage of patients (%) alive at 6, 12 and 24 months in both cohorts: percentage of patients alive at 6 months, 12 month and 24-month considering date of inclusion. The final statistical analysis of this endpoint is expected to be performed within 6 months after database closure expected at 24 months after last patient inclusion, however interim analysis might be performed when analysing other primary variables.

**Toxicity of the combination until local treatment:** Number of patients with adverse events and serious adverse events, changes in laboratory values, vital signs, electrocardiograms (ECGs), LVEF (MUGA (Multigated Acquisition Scan) / echocardiogram) and assessment of physician, dermatological and ocular examinations graded according to the National Cancer Institute (NCI) Common Terminology Criteria for Adverse Events (CTCAE) v 4.03 until local treatment (local treatment D1). It will be studied using descriptive statistics techniques, such as frequency tables and contingency tables. The final statistical analysis of this endpoint is expected to be performed within 6 months after database closure expected at 24 months after last patient inclusion, however interim analysis might be performed when analysing other primary variables.

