### Figure: intracranial Progression Free Survival (PP Cohort 2)

# 4.7. Extracranial Progression-free survival (ePFS).

Extracranial Progression-free survival (PFS), defined as the time from inclusion (first dose of treatment) until extracranial tumour progression (RECIST 1.1) or death. Patients without any of the previous events are censored at the date of the last available tumor assessment.

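### Scheduled scans end at the first progression at either site, but iPFS and ePFS count any later death and censor survivors at their last scan; the two documents' iPFS censoring rules conflict, and any-site PFS is never estimated

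*Combined protocol and SAP*

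**What the plan says.** **Imaging.** Protocol 5.3 says that patients with progression on brain MRI and/or body CT at the first evaluation "will discontinue study treatment and will continue in the study for OS follow-up". It then states in general: "After progression, patients will be followed only for overall survival". The OS follow-up paragraph of protocol 8.1 agrees: "After disease progression all patients will be monitored to determine subsequent antineoplastic treatments and survival". Protocol 8.2, on follow-up after treatment ends, adds: "Subjects who have switched to an alternative treatment do not perform a formal follow-up, except to record the date of the death". None of these rules depends on which site progressed.

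There are two qualifications. A patient with an unirradiated intracranial complete response and later brain-only progression may receive local treatment and stay on study drug; later scans are not specified (synopsis, protocol 5.3). Investigators may also order unscheduled assessments (protocol 8.1).

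**Analysis.** SAP 4.6 counts intracranial progression or death. SAP 4.7 runs ePFS "until extracranial tumour progression (RECIST 1.1) or death". Both use the same censoring sentence: "Patients without any of the previous events are censored at the date of the last available tumor assessment". Neither limits the gap between last scan and death, and neither says what to do when the other site progresses first.

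Protocol 10.2 also counts death from any cause in iPFS, but censors living, progression-free patients at last follow-up rather than at the last assessment. For the extracranial endpoint it specifies the "percentage of patients free of progression by RECIST 1.1 at 6 months (week 24), 12 months (week 48) and 24-month (week 96") and does not mention death.

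No objective, protocol endpoint or SAP table covers progression at any site or death.

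**The concern.** Take two patients with extracranial-only progression at the week-16 scan (month 3.7) and no brain MRI afterwards. One dies 10 months later: under SAP 4.6 this is an iPFS event at month 13.7, and the patient counts as intracranially progression-free at 12 months on no brain imaging after month 3.7. The other is alive at the data cut and is censored at month 3.7. Their brain data are the same. Later survival decides which rule applies, so the censoring is informative. ePFS has the mirror problem after intracranial progression.

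Two errors pull in opposite directions. Progression missed at the unscanned site is dated late, at death, which raises the curve. Unscanned patients who die count as events while unscanned survivors leave the risk set early, which lowers it. A reader of the final report could not tell which dominates.

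At stake are the 6-, 12- and 24-month percentages and medians for both site-specific endpoints, and the absence of the one progression endpoint whose definition matches when scheduled scanning ends.

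**Working it through.** **Plan's own figures.** None is given for iPFS, ePFS or PFS. The only sizing is for response (protocol 10.1): n = [(1.645·√0.24 + 0.842·√0.24)/0.20]² = 37.1, so 38; 38/0.8 = 47.5, so 48. It reproduces and does not depend on this point.

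**Inputs from the documents.** Scans every 8 weeks to 12 months, then local practice; OS-only follow-up after progression; recruitment 36 months and follow-up 24 months (protocol 8.3), so a final cut falls 24–60 months after entry. A cut at 3–39 months represents an interim look, which protocol 10.2 allows.

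**Assumptions.** The documents give no site-specific rates. Assumed medians: intracranial progression 9–12 months, extracranial 12–16, survival after progression 5–12, and 80 months for death without progression. Scans after week 48 are taken as 12-weekly. There are 400,000 simulated patients per setting. The reference is the same endpoint with scans of that site continued after other-site progression.

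12-month iPFS, % (medians in the order intracranial / extracranial / survival after progression):

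| Setting; cut (months) | Scans continued | SAP rule | Protocol 10.2 rule |
|---|---|---|---|
| 9/16/5; 24–60 | 30.1 | 32.4 (+2.3) | 32.5 (+2.4) |
| 12/12/6; 24–60 | 36.2 | 39.2 (+3.0) | 39.5 (+3.3) |
| 9/16/12; 24–60 | 34.3 | 38.0 (+3.7) | 39.2 (+4.9) |
| 9/16/5 with frailty | 31.6 | 33.1 (+1.5) | 33.3 (+1.7) |
| 9/16/5; 3–39 | 29.8 | 31.1 (+1.3) | 32.7 (+2.9) |
| 9/16/12; 3–39 | 34.1 | 35.6 (+1.5) | 39.2 (+5.1) |

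- **12-month ePFS, SAP rule:** +2.5, +2.9 and +3.9 points in the three mature settings (for example 50.5 against 46.6); +0.9 and +0.3 with the early cut.
- **24 months, early cut, SAP rule:** iPFS 6.9 against 7.0 and 9.9 against 10.0; ePFS 8.4 against 9.2 and 14.1 against 17.1 (−3.0).
- **Protocol 10.2 rule:** upward in every setting, about +1 to +9 points across 6, 12 and 24 months for both endpoints.
- **Patients affected:** 23–38% have unobserved brain status after extracranial progression; 38–53% have the mirror gap for ePFS.

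**Acceleration after stopping.** These settings keep the intracranial rate unchanged after extracranial progression. A separate check widened the medians (extracranial 9–16 months, survival after progression 5–12) with the mature cut. With no acceleration, 12-month iPFS was overstated by 2.6 to 5.1 points in five of six settings and by 6.0 in the sixth. With a 4-month intracranial median after stopping, the overstatement was 4.6 to 12.3 points.

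**The case against.** The strongest reply is that these are secondary, descriptive endpoints, that counting death in a progression-free survival endpoint is conventional, and that the likely error is small against sampling error: an exact 95% interval around 22/63 is 23–48%, and around 5/15 is 12–62%. That stands as a limit on severity. It does not remove the rule conflict or the missing endpoint.

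Several stronger readings are tempting and are not supported.

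- **Imaging stops altogether.** Only scheduled in-study imaging ends. The complete-response exception and discretionary scans remain, and SAP Tables 51–52 have a category for progression at both sites.
- **Any-site PFS is the one fully observed endpoint.** OS is also followed and is estimated (SAP 4.5). Any-site PFS is itself scanned by local practice after 12 months.
- **Both estimates are biased upward.** Under the SAP rule the sign depends on the assumed rates, the time point and the data cut.
- **The gap between any-site PFS and iPFS measures the error.** The simulated medians were 5.5–6.2 months for any-site PFS and 7.4–9.2 for iPFS under the SAP rule, but any-site PFS is shorter by construction.
- **The trial cannot answer its own question.** The rationale points to "the apparently short progression free survival in the main cohort" of an earlier trial (5.6 against 11 months) and asks whether local therapy could prolong responses. Duration of intracranial response is an endpoint, and a single-arm trial could not settle the causal question even with any-site PFS. The rationale does not say which site its PFS figures cover.
- **Protocol 10.2 excludes death from the extracranial endpoint.** It is silent on death.

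**Conclusion.** The point holds in this limited form. For patients whose first progression is at the other site, the SAP makes later survival decide between an event dated at death and censoring back at the last scan. The text alone establishes that.

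The size is not established by the documents and rests on assumed hazards. For 12-month iPFS under the SAP rule with mature follow-up, the overstatement is roughly 2 to 5 points without acceleration, and up to about 12 if intracranial progression speeds up sharply after study treatment stops. Across the settings without acceleration in the main simulation, both endpoints and all time points, the net error ran from about −3 to +4 points.

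The conflict between protocol 10.2 and SAP 4.6 on the iPFS censoring date is a plain contradiction, and last follow-up was the worse of the two choices in the simulations. The absence of any-site PFS is a gap worth closing. This should be corrected, but it does not threaten the primary analysis.

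**What to change.** 1. Add any-site PFS (first of intracranial progression, extracranial progression or death) in ITT, by cohort and pooled.
2. Add the cumulative incidence of first failure, with intracranial progression, extracranial-only progression and death without progression as competing events. Derive it from the recorded progression and death dates: Table 51 shows type of progression but not the order of events. This supplements iPFS and ePFS and does not replace them, because it ignores progression at the second site.
3. Keep iPFS and ePFS, with a sensitivity analysis that censors at the last scan of that site any death falling after other-site progression or beyond a fixed interval since that scan. In year 1 the interval could be two scan intervals plus the window (16 + 1 = 17 weeks); state one for after month 12, when the protocol fixes none. Present it as a sensitivity analysis only: censoring all such patients at other-site progression gave 36.2% in the first setting above, against 30.1% with continued scans, so it is not a correction.
4. Use one iPFS censoring date in protocol 10.2 and SAP 4.6. State how other-site progression is handled, and whether death counts in the percentage free of extracranial progression (protocol 10.2 against SAP 4.7). In the supplementary table of iPFS by radiotherapy, say whether death without previous progression refers to intracranial or any-site progression.

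The cost is a few tables from data already collected, with no extra imaging. The primary response rate and the sample size do not change.
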